2.2. Structure of the interview

The interview will be conducted by telephone (or internet) or may be face-to-face/in-person at a time chosen by the patient (and / or parent) and the interviewer. Each interview will last approximately one hour.

The interview is divided into three stages:

- **Introduction and Presentation of the study (5 minutes)** : Presentation of the interviewer, presentation of the purpose of the study and conduct maintenance.
- **Exploratory interview (50 minutes)**: It's important to use semi-directive interview techniques: let the patient (and / or their parent) speak spontaneously, then use probes to obtain information about specific topics and a complete understanding/knowledge of the patient's (and / or their parent's) experiences. All of the main themes described in the guide should be addressed, but it is not mandatory to follow the sequence exactly as written in this guide. If a topic is discussed earlier by the patient (and / or parent) during the interview, it can be explored and discussed at that time. The patient (and / or their parent) may take several minutes to answer the question. The interviewer will need to anticipate this possibility by giving sufficient time to the patient (and / or parent) to respond. The interview guide provides a non-exhaustive list of topics. Themes and probes are there as an indication and reminder of what needs to be explored during the interview.
- **End of the interview (5 minutes)**: Questions on the socio-demographic data form (separate document) should be answered by the patient (and / or their parent) at the conclusion of the interview.

2.3. Notification of an adverse event

During the interview, if the patient (and / or their parent) spontaneously reports an adverse event, the interviewer should notify the appropriate person(s) at the investigational site so that appropriate documentation, reporting, and follow up can be initiated as appropriate.

3. Baseline Interview Guide - Content

a) Introduction and purpose

- Thank the patient (and / or their parent) for agreeing to participate in the interview.
- Introduce the company, ICONi: a company that works with pharmaceutical companies to better understand diseases, their treatments and their impact on patients' lives.
- Introduce the objectives for the interview: To learn about the experiences of the patient with distal renal tubular acidosis and its treatment.

b) Confidentiality

- Remind the patient (and / or their relative) that:
 - The interview will be transcribed and analyzed confidentially and anonymously: anything that could identify the patient (and / or his parent) will be deleted (name, location ...);
 - The interview will be analyzed together with all other interviews conducted.

c) Conduct of the interview and registration

- Let the patient (and / or their parent) know that:
 - The duration of the interview: Approximately one hour;
 - you would like to record the interview to facilitate the conversation (and ask for their verbal agreement to record the conversation);
 - the recording is confidential and only accessible to the research team;
 - the recording will be destroyed at the end of the study;
 - he /she can stop the interview at any time and / or not to answer certain questions;
 - he/she should feel free to answer the questions honestly and not to be worried about or afraid to say what they think (s).

d) Questions

- Check that the participant (s) consents to be interviewed.
- Give the patient (and / or parent) the opportunity to ask questions before starting the interview.

e) Start recording

- Announce:
 - The date
 - The identification number of the patient
 - The participants): patient and / or parent
 - The type of interview (baseline)
- Obtain and record the consent of the patient to record the interview.

4. Exploratory interview

Theme 1: Daily Distal Renal Tubular Acidosis

- Diagnosis
 - When you were first diagnosed? *Date, moment*
 - *Symptom (s) that prompted the consultation* – Was there anything specific related to your dRTA that you were experiencing that made you decide to go to your doctor
 - *Health professional (s) consulted* – How long did it take and who diagnosed your dRTA?
 - *Feelings, emotions* – How did you feel and what did you think about it when you learned about the diagnosis?
- Evolution of dRTA – Have your experiences with dRTA changed over time? How so?
 - Have you experienced any physical symptoms that you think are caused by dRTA? (*Symptom (s): muscle weakness pain, bone or growth problems, feeling ill, weak*)
 - Have you experienced anything emotionally or mentally related to dRTA? *Feelings, emotions*
- Impact of dRTA on your quality of life
 - *Activities of everyday life*
 - *At school, at work*
 - *Relations with family, friends*
 - *Sports, leisure activities*
 - *Sleep*
 - *Emotions, mood*

Theme 2: Treatment of daily dRTA

- Description of treatment before entering the study Do you think of the things you use for your dRTA as medicines? Why/Why not?

- *Preparation (set-up)* – Have the products/medications you used to treat your dRTA required much preparation? Please tell me in as much detail as you can, how you prepare and take your product(s)
 - *Administration: intake (taste, texture), number of times actually taken per 24h* – Take me through a typical day (24 hour period) in your life describing where, when, how you would typically treat your dRTA? Does your routine vary from day-to-day?
- How often in a 24hr period do you take the medication? How do you know when it is time to take your product/medication? How, if at all, do you keep track of how often you dose?
 - Adherence / monitoring of the treatment
 - *Reasons / motivations to follow (or not) the prescription*
 - *If applicable: Adaptation of the prescription by the patient*
 - Using a scale from 1-10 with 1 = not satisfied at all and 10 = completely satisfied, How satisfied would you say you are with your current medication or product?
 - *Factors / reasons for satisfaction (or dissatisfaction)- list all*

Theme 3: The study for ADV7103

- Motivations to enter the study – What made you decide to participate or have your child participate in the study?
- Treatment expectations on ADV7103 treatment – Please list all the benefits and positive characteristics that the ideal medication or product for treating dRTA should have? Reviewing the list, how close does your current product or medication come to meeting each of these on the list? Where does it fall short?

5. End of the interview

5.1. Sociodemographic data form

- Complete with the patient (and / or parent) the Sociodemographic Data Form (separate document).

5.2. Conclusion

- Ask the patient (and / or their parent) if they / they wish to add anything.
- Thank the patient (and / or their parent) for their participation.
- Remind the patient (and / or their parent) that they will be contacted again in about 8 weeks (End of Stabilization Period) for a second telephone conversation.

Stop recording: make sure that the interview is properly recorded. In the event that the interview has not been recorded or is of poor quality, report the discussion.

Protocol and Interview Guide

Patient and Parent

Post Stabilization

Version 1.0

1. Context and objectives

Advicenne is currently developing ADV7103, an innovative formulation of potassium citrate in the form of micro-tablets for the treatment of distal renal tubular acidosis.

Distal renal tubular acidosis (dRTA) is a condition characterised by a renal defect in hydrogen ion secretion in the distal renal tubules, inducing a hyperchloremic metabolic acidosis (low blood pH = less than 7.35) with no urine acidification.

Usually in non-dRTA subjects, the blood pH is about 7.4 corresponding to a blood concentration of bicarbonate of 21 to 28 mmol/L. A metabolic acidosis corresponds to a blood pH below 7.35 with a bicarbonate blood concentration lower than 22 mmol/L (or 22 mEq/L) (Chan, Scheinman et al. 2001).

Major biological signs of dRTA are usually a hyperchloremic metabolic acidosis, hypokalaemia and hypercalciuria, with a high pH of urine (>6.5), inducing nephrocalcinosis or lithiasis without treatment. In most cases, the condition causes osteomalacia in adults and short stature to rickets in infantile forms. In some genetics forms, deafness could be linked to mutation.

Distal renal tubular acidosis could be an inherited condition induced by genetic mutations or a secondary condition related mainly to autoimmune diseases (e.g. primary Sjögren's syndrome, systemic lupus erythematosus, primary biliary cirrhosis, autoimmune hepatitis).

There is no curative treatment of dRTA. This blood pH dependence of symptoms is the basis of the medical treatment of dRTA, which relies on alkalisation to maintain a blood pH of 7.4 with a bicarbonate blood concentration above 22 mmol/L (Chan, Scheinman et al. 2001).

Alkali therapy, as sodium bicarbonate and potassium bicarbonate or tripotassium citrate, is used in dRTA to stabilise correction of metabolic acidosis and improves clinical spectrum of patient inducing a minimisation of stone risk and a better growth if treatment is early instituted. No effect was noticed on deafness. The aim of alkali therapy is to achieve a normal blood bicarbonate concentration (22 to 24 mEq/L). A continuous treatment is necessary to observe clinical improvement, using a mean alkali therapy of 1-2 mEq/kg/day in adults and of 4-8 mEq/kg/day in children where bicarbonate losses are frequently higher than in adults (Chan, Scheinman et al. 2001; Rodriguez Soriano 2002).

Currently available potassium citrate formulations exhibit low adherence characteristics, particularly in the pediatric population. In fact, the doses must be administered up to every 6 hours in 24 hours, including an administration during the night. In addition, the formulations involve any side effects are gastro-intestinal to and have a bitter taste.

Comparatively, ADV7103 has three advantages, it: (1) is tasteless and easy administration, particularly in young children, (2) reduces gastrointestinal side effects with intestine, and (3) requires only two doses per 24 hours.

The ARENA clinical development program of ADV7103 for dRTA consists of

- B21CS (ARENA 1) and B22CS: ARENA 1 is a cross-over study comparing dRTA standard of care to ADV7103 and the associated long-term extension study. ADV7103 proved to be non-inferior to SoC in maintaining serum bicarbonate levels above the lower limit of normal, and in fact,

demonstrated superiority on this parameter. ADV7103 also maintained serum potassium levels in a safe range and showed good tolerability compared to SoC.

- B23CS (ARENA 2) and B24CS: ARENA 2 is a randomized withdrawal study comparing the ability of ADV7103 to prevent the development of metabolic acidosis compared to placebo, over 6 days. B24CS is the associated long-term open label roll-over study.

As part of the B23CS (ARENA 2) study, Advicenne commissioned MAPI/ICON to conduct qualitative research based on semi-structured interviews at the beginning of the study (" baseline "), and then at the conclusion of the stabilization period, approximately 8 weeks later. Over the course of the two interview, the intent is to explore the patient's perspective on :

- dRTA and treatments that patients currently use to manage dRTA (standard of care/SOC) and the impact of dRTA and current treatment options on patients' daily lives;
- patients' attitudes, beliefs and behaviors related to dRTA and its treatment;
- how dRTA itself and how they have treated their dRTA have evolved over time.

This guide presents the instructions and the method to be used to conduct interviews at the end of Stabilization ("Period 2").

2. Methods

2.1. The Interviewer

The roles and responsibilities of the interviewer are detailed below.

Before and at the beginning of the interview :

- Schedule an appointment with the patient (and / or their parent) for an interview;
- Offer the patient (and / or his or her parent) to use a video platform to perform the interview (Skype, WebEx ...) ;
- Ensure that the interviewer and the patient (and / or their parent) are in quiet locations, respectively, where the conditions guarantee the free expression of the patient (and / or their relative) and confidentiality, without interruption;
- Ensure the proper operation of the recording device/system; if the recording equipment uses batteries, use new batteries at each interview;
- Receive training and know the procedure to follow in case of spontaneous notification of adverse effects;
- Check that the patient (and / or their parent) has been informed (s) and has / have agreed to participate in the interview;
- Recall the purpose of the interview to the patient (and / or parent), and what is expected of him / her / them;
- Remind the patient (and / or their parent) of the confidentiality and anonymity of the information they / he / she will report; his / their answers will be forwarded only to those involved in the study and will not be linked to his / her name (s);

- Remind the patient (and / or their parent) that the interview is being recorded and ask for verbal consent before starting the interview and while recording;
- Answer any questions that the patient (and / or their parent) may have before starting the interview.

After the interview :

- Check the recording; in case the interview has not been recorded, take detailed notes based on recent memory (if convenient and not distracting, notes should also be taken during the interview);
- Rename the audio file : 060482 _ [patient ID] _ [patient +/- parent] _ stabilization_Date [DD-MMM- YYYY]. Download the audio file to the secure server. If notes have been taken, the annotated document must be scanned, renamed as before and uploaded to the secure server along with the audio file ;
- Classify the adverse reaction reporting report in the event that the patient (and / or their parent) has spontaneously reported an adverse reaction to a sponsor product during the course of the interview. The investigator must report an adverse event according to the procedure described in section 2.3 of this document.

2.2. Structure of the interview

The interview will be conducted by telephone (or internet) or may be face-to-face/in-person at a time chosen by the patient (and / or parent) and the interviewer. Each interview will last approximately one hour.

The interview is divided into three stages:

Introduction and Presentation of the study (5 minutes): Presentation of the interviewer, presentation of the purpose of the study and conduct maintenance.

Exploratory interview (50 minutes): It's important to use semi-directive interview techniques: let the patient (and / or their parent) speak spontaneously, then use probes to obtain information about specific topics and a complete understanding/knowledge of the patient's (and / or their parent's) experiences. All of the main themes described in the guide should be addressed, but it is not mandatory to follow the sequence exactly as written in this guide. If a topic is discussed earlier by the patient (and / or parent) during the interview, it can be explored and discussed at that time. The patient (and / or their parent) may take several minutes to answer the question. The interviewer will need to anticipate this possibility by giving sufficient time to the patient (and / or parent) to respond. The interview guide provides a non-exhaustive list of topics. Themes and probes are there as an indication and reminder of what needs to be explored during the interview.

End of the interview (5 minutes): Questions on the socio-demographic data form (separate document) should be answered by the patient (and / or their parent) at the conclusion of the interview.

2.3. Collecting and Reporting Adverse Events

During the interview, if the patient (and / or their parent) spontaneously reports an adverse event, the interviewer should notify the appropriate person(s) at the investigational site so that appropriate documentation, reporting, and follow up can be initiated as appropriate.

3. Interview Guide - Content

a) Introduction and purpose

Thank the patient (and / or their parent) for agreeing to participate in the interview.

Introduce the company, ICON: a company that works with pharmaceutical companies to better understand diseases, their treatments and their impact on patients' lives.

Introduce the objectives for the interview: To learn about the experiences of the patient with distal renal tubular acidosis and its treatment.

b) Confidentiality

Remind the patient (and / or their relative) that:

The interview will be transcribed and analyzed confidentially and anonymously: anything that could identify the patient (and / or his parent) will be deleted (name, location ...);

The interview will be analyzed together with all other interviews conducted.

c) Conduct of the interview and registration

Let the patient (and / or their parent) know that:

- duration of the interview: Approximately one hour;
- you would like to record the interview to facilitate the conversation (and ask for their verbal agreement to record the conversation);
- the recording is confidential and only accessible to the research team;
- the recording will be destroyed at the end of the study;
- he /she can stop the interview at any time and / or not to answer certain questions;
- he /she should feel free to answer the questions honestly and not to be worried about or afraid to say what they think (s).

d) General Questions

Check that the participant (s) consents to be interviewed.

Give the patient (and / or parent) the opportunity to ask questions before starting the interview.

e) Start recording

Announce:

- The date
- The identification number of the patient
- The participant(s): patient and / or parent
- The type of interview : " baseline "
- Obtain and record the consent of the patient to record the interview.

4. Stabilization interview guide - Content

Theme 1: Experiences with Distal Renal Tubular Acidosis (dRTA)

What has changed, if anything, since you started taking the study medication?

If not discussed, probe on any changes in physical symptoms or impacts of dRTA that may have been mentioned at baseline.

Theme 2: Experiences with taking ADV7103

Is there anything in particular that you remember about the new study medication when you first started taking it during the clinical study?

Preparation (set-up) – What do you have to do, if anything, to prepare to take the study medication before you take it? Is this different than how it was with the medication you took before you started the clinical study? How so?

Please list all the things that are the same and all the things that are different about the new study medication as compared to the medication you took before the clinical study? If not mentioned, probe taste, texture, doses in 24 hrs, how you feel after you take it.

Adherence / monitoring of the prescription – how easy or difficult do you think it will be for you to follow the directions and take the medication as directed when you are no longer in the clinical study? Why?

Reasons / motivations to follow (or not) the prescription – During the baseline interview, if the patient mentioned reasons why he/she took the medication less often than he/she was supposed to take it, ask whether those same reasons would apply to the study medication.

Theme 3: Overall satisfaction, expectations for treatment, and meaningful improvements

Satisfaction

Using a scale from 1-10 with 1 = not satisfied at all and 10 = completely satisfied, how satisfied would you say you are overall with the study medication?

Factors / reasons for satisfaction (or dissatisfaction)- list all

Expectations

Overall, would you say the study medication has:

- Not met my expectations/is not as good as I thought it would be
- Has met my expectations/ about the same as I thought it would be
- Has exceeded my expectations/ is better than I thought it would be

Why did you say the study medication (did not meet, met, or exceeded) your expectations?

Meaningful Improvements

What, if any improvements, have you experienced on the study medication that are meaningful to you?

5. End of the interview

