11. ASSESSMENT OF SAFETY

11.1. Safety Parameters

The safety of ADV7103 will be assessed, in part, using parameters included in Section 10.2.1 through Section 10.2.11.7. Adverse events (AEs), defined in Section 11.2.1, will be captured during every study encounter following signature of the informed consent form.

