11.3. Relationship of Adverse Event to Study Product

An Investigator who is qualified in medicine must make a determination of relationship to the study product for each AE. [Table 3](#) includes the criteria for determining relationship between the AE and the study product.

Table 3: Criteria for Determining Causal Relationship to the Study Product

Causal Relationship to the Study Product	Criteria for Determining Causal Relationship
Definitely Related	There is clear evidence to suggest a causal relationship, and other possible contributing factors can be ruled out. The clinical event, including an abnormal laboratory test result, occurs in a plausible time relationship to administration of the study product and cannot be explained by concurrent disease or other devices, drugs, or chemicals.
Possibly Related	There is some evidence to suggest a causal relationship (eg, the event occurred within a reasonable time after administration of the study product). However, the influence of other factors may have contributed to the event (eg, the subject's clinical condition, other concomitant events). Although an adverse effect may rate only as "possible" soon after discovery, it can be flagged as requiring more information and later be upgraded to probable or certain as appropriate.
Unlikely Related	A clinical event, including an abnormal laboratory test result, whose temporal relationship makes a causal relationship improbable (eg, the event did not occur within a reasonable time after administration of the study product) and in which other drugs or chemicals or underlying disease provide plausible explanations (eg, the subject's clinical condition, other concomitant treatments).
Not Related	A clinical event, including an abnormal laboratory test result, which occurs when the subject was not exposed to the study product or, another cause is obvious and in which there is sufficient information that the etiology of the event is not related to the study product.

If the relationship between the AE and the study product is determined to be "definitely related" or "possibly related," the AE will be considered to be related to the study product for the purposes of expedited regulatory reporting.

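### Interviewers must tell the site only about adverse events reported spontaneously, although the Post Stabilization guide probes for symptoms, so an event disclosed only on probing has no stated route to the site

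*Combined protocol and SAP*

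**What the plan says.** The interviews are run by a vendor's trained interviewers (Section 10.2.16). The second is held near the last Stabilization Phase visit.

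- **Duty to notify.** Section 2.3 of both guides sets the condition: "if the patient (and / or their parent) spontaneously reports an adverse event, the interviewer should notify the appropriate person(s". The persons meant are those at the investigational site.
- **Interview technique.** Section 2.2 of both guides tells the interviewer to "let the patient (and / or their parent) speak spontaneously, then use probes to obtain information about specific topics".
- **Symptom probes.** In Section 4 of the Post Stabilization guide, Theme 1 opens with a general question about what has changed. It then prompts on changes in physical symptoms, or in dRTA impacts, raised at baseline. Theme 2 adds: "If not mentioned, probe taste, texture, doses in 24 hrs, how you feel after you take it".
- **Post-interview step.** Section 2.1 of both guides describes classifying a report when the patient "has spontaneously reported an adverse reaction to a sponsor product during the course of the interview". Its next sentence returns to adverse events and refers to Section 2.3.
- **Protocol body.** Section 11.1 says that AEs "will be captured during every study encounter following signature of the informed consent form". Under Sections 10.2.14 and 11.5.1 the site asks about AEs in a general way and suggests no symptoms.

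**The concern.** The second interview is designed to draw out how subjects have felt on ADV7103, but its safety instruction covers only what they volunteer. An interviewer who follows the guide exactly could hear of a new symptom in reply to a probe and have no instruction to tell anyone at the site.

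Two things depend on that information. TEAE frequency by study period is a secondary objective (Section 5.2). At about the same time the Investigator must judge whether safety and tolerability are acceptable for randomization (Section 6.2.2.2), ahead of a withdrawal period that may be conducted at home.

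**Working it through.** The documents state no figure on interview-derived AEs, so the check is a comparison of texts.

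1. **Trigger.** A spontaneous report is the only condition for notification in either guide. No other sentence says what to do with an AE that comes out in another way.

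2. **Meaning of the word.** Section 2.2 makes spontaneous speech and probing two successive modes of the interview. Section 2.1 also describes interviewer training in terms of spontaneous notification. An interviewer would naturally read a probed answer as falling outside the duty.

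3. **What is elicited.**
   - Baseline guide, Theme 1: physical symptoms the patient attributes to dRTA, asked near Visit 1 while on standard of care. This is largely disease history, not treatment-emergent.
   - Post Stabilization guide, Theme 1: changes in symptoms during ADV7103 treatment, first through an open question and then a prompt.
   - Post Stabilization guide, Theme 2: how the subject feels after a dose. This is the most direct tolerability probe.

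4. **Against Section 11.1.** That section sets no limit on how an AE comes to be mentioned. The schedule in Section 17.1 lists the interview among the activities of Visits 1 and 2 and of early withdrawal, under the heading of study encounters. Section 2.3 of the guides is therefore the narrower rule.

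5. **Other routes to the site.** Visit 2 includes AE review and a targeted physical examination (Section 10.3.2.1). The questionnaires add a gastrointestinal tolerability rating (Section 10.2.15.5.5) and, from age 13, the side-effect dimensions of ACCEPT and TSQM. These help, but three gaps remain:
   - The site's AE question is general, and the questionnaires are not AE collection.
   - The interview is only near the visit and may come after the AE question.
   - No step compares interview content with the AE record. Recordings are destroyed at the end of the project and identifying details are removed from transcripts.

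6. **Which results are touched.** The second interview precedes Period 3. An early-withdrawal interview takes place only where no second interview was held. The effect therefore falls mainly on Period 2, which is single-arm and summarized descriptively (Section 12.4).

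7. **Size.** The number of subjects with a missed AE would be N × p × q. Here N is the number interviewed, at most about 40 because that many enter Period 2 and interviews may be declined. The term p is the proportion with a Period 2 AE, and q is the share of those whose AE emerges only on probing and is not captured elsewhere. The documents give neither p nor q, so no count follows.

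**The case against.** The strongest defence is that the restriction matches the protocol's method. Sites deliberately suggest no symptoms, so AE data are unsolicited throughout. Adding probed events would introduce solicited reporting in Period 2, only in subjects who accept an interview, with no counterpart in Period 3. The point about comparability stands, but it is a reason to label such events, not to leave the site uninformed. The defence is also right that the Visit 2 procedures cover part of the gap, and that forwarding everything said in the Baseline interview would send long-standing dRTA history to sites as possible AEs.

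Some stronger readings are tempting but not supported:

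- **A causality filter in the interviewer's hands.** A reader might infer this from the words "spontaneously reported an adverse reaction to a sponsor product during the course of the interview" in Section 2.1, and set it against Section 11.3, which reserves causality for a medically qualified Investigator. The phrase governs classification after the interview, and the text then defers to Section 2.3, which covers any AE. It is an inconsistency of terms.
- **A conflict with the AE definition.** Section 11.2.1.1 says an AE need not be causally related. It says nothing about how the AE was elicited.
- **A breach of the 24-hour rule for serious events.** Section 11.5.2 sets that clock for the Investigator from learning of the event. It sets none for interviewers.
- **Fifty minutes of probing.** That time is the whole exploratory part of the interview, which starts with free speech.

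**Conclusion.** The gap is real but modest. As written, an AE disclosed only on probing in the Post Stabilization interview, or in an early-withdrawal interview, has no stated route to the site, and this is narrower than Section 11.1. Period 2 AE frequency may be understated, and the Investigator may lack tolerability information before randomization.

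This rests on two assumptions: that interviewers apply the guides literally, and that some events surface on probing that the site's general question does not bring out. The documents support the first by their own contrast of terms and give no evidence on the second. It would therefore go too far to say that the counts are too low, or to attach a number of subjects. The primary endpoint is not involved, and the randomized Period 3 safety comparison is little affected.

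**What to change.** - In Section 2.3 of both guides, replace the spontaneous-report condition with: *mentions an adverse event, whether volunteered or in answer to a question, and whether or not thought related to treatment*. Limit it to events that began or worsened after informed consent, so that prior dRTA history is not forwarded.
- Use the term adverse event consistently in Sections 2.1 and 2.3 of both guides.
- Have the interviewer pass the information to the site promptly, so that the site can apply Sections 11.2.1.1, 11.3 and 11.5.2.
- Add an eCRF flag for AEs whose source was an interview, and show frequencies by period with and without them.

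The cost is wording in two guides, a short interviewer briefing and one eCRF field. The small downside is that Period 2 gains an AE source that Period 3 lacks. The flag deals with that.
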